3 STATISTICAL METHODOLOGY

3.1 General Considerations

The statistical analysis of the data obtained from this study will be performed using SAS® version 9.4 or higher.

Data collected in this study will be documented using summary tables and subject data listings. Continuous variables will be summarized using descriptive statistics, specifically the number of non-missing observations, mean, standard deviation, median, minimum, and maximum. Categorical variables will be summarized using the frequency count and the percentage of participants in each category. For continuous data, the minimum and the maximum will use the same decimal place accuracy as the raw data. The mean, median, and standard deviation will use one more decimal place than the raw data. For categorical data, percentages will be reported to one decimal place.

Summary statistics will be presented by randomized or actual treatment group for the Primary Study Period. The key efficacy and selected safety endpoints will be summarized for the Primary Study Period.

No hypothesis tests will be performed.

3.1.1 Study Day

Study day will be calculated from the date of first dose of study drug, as actual visit date – first dose date for dates before the first dose date and +1 for dates on or after the first dose date. The day of the first dose of study drug will be Day 1, and the day immediately before and after Day 1 will be Day -1 and Day 2.

For participants who crossed over, the first dosing date of the Cross-Over Period will be Day 1' for that period. Study day of the Cross-Over Period will be calculated as actual visit date in the Cross-Over Period – Cross-Over Period Day 1' + 1.

3.1.2 Analysis Visits

Subject visits might not occur on protocol-specified days. Therefore, for the purpose of analysis, all scheduled, unscheduled, and early termination visits will be assigned to analysis visits according to the analysis windows ([Appendix 1](#)) based on study days. If there is more than 1 assessment in an analysis window, the assessment closest to the target day will be used in the analysis. If there are 2 assessments in a window equidistant from the target day, the later assessment will be used in the analysis.

3.1.3 Definition of Baseline

Baseline is defined as the last non-missing measurement prior to the first dose of study treatment. This can be on Day 1 as long as the measurement is taken prior to the first dose.

3.1.4 Handling of Dropouts and Missing Data

In general, data will be analyzed and presented as observed and will not be imputed for the analysis of efficacy and safety, unless otherwise specified. The missing data handling for the primary efficacy endpoints is discussed in [Section 3.4](#).

In case the start and end dates for adverse events and concomitant medications/procedures are missing or incomplete, the missing component(s) will be assumed as the most conservative value possible. For example, AEs with missing start dates, but with stop dates either overlapping into the treatment period or missing, will be counted as treatment-emergent, taking the worst-case approach. When partial dates are present in the data, both a partial start date and/or a partial stop date will be evaluated to determine whether it can be conclusively established that the AE started prior to the start of study treatment or ended prior to the start of study treatment. If the above cannot be conclusively established based on the partial and/or present dates, then the AE will be considered as treatment-emergent. Actual data values as they appear in the original case report forms (CRFs) will be presented in the data listings.

3.2 Analysis Populations

3.2.1 Intent-to-Treat (ITT) Population

The ITT Population will include all randomized participants and will be used for listings.

3.2.2 Modified Intent-to-Treat (mITT) Population

The mITT Population will include all randomized participants who receive at least one dose of posoleucel or placebo. All efficacy endpoints will be analyzed based on the mITT Population. Participants will be analyzed according to the randomized study treatment. The efficacy analysis will be based on the mITT population.

3.2.3 Safety Population

The Safety Population will include all participants who receive any amount of posoleucel or placebo. All safety analyses will be based on the Safety Population. Participants will be analyzed according to the actual study treatment received. All safety analyses will be based on the Safety Population.

3.3 Participant Data and Study Conduct

3.3.1 Participant Disposition

Participant disposition information will be summarized using the Enrolled Population (all participants who sign the informed consent form). The numbers and percentages of participants who were screened, screen failure along with the reasons of screen failure, randomized, randomized and not dosed, dosed, completed study drug, discontinued study drug early along with the reasons for early discontinuation of study drug, entered Cross-Over, completed the study, and discontinued the study early along with the reasons for early discontinuation of study. The study and study drug disposition will be summarized for the Primary Study Period and the Cross-Over Period. The numbers and percentages of recurrence participants will be summarized. The number of participants who received any study treatment will be summarized by the number of infusions.

By-participant listings will also be provided for participant disposition.

3.3.2 Demographic and Baseline Characteristics

Demographic (age and age subgroups [e.g. 0 to <2y; 2-<6y; 6 to <12y; 12 to <18; <65, >=65, sex, race, and ethnicity), baseline characteristics (height, weight, BMI), and randomization stratification factors will be summarized with descriptive statistics or counts and percentages of participants as appropriate for mITT Population.

The following disease characteristics will also be summarized using frequencies and percentages or descriptive statistics:

- Baseline Weight (kg) (overall, Age >/≤ 18 years)
- Baseline Height (cm) (overall, Age >/≤ 18 years)
- Baseline BMI (kg/m²) (overall, Age >/≤ 18 years)
- Baseline Target Organ Disease Diagnosis, n (%)
- Screening AdV Viremia, n (%)
- Baseline AdV Viremia, n (%)
- Baseline Viremia, n (%)
- Use of Cidofovir at Baseline, n (%)
- Hematopoietic Cell Transplantation Donor Type, n (%)
- Time (Days) from Hematopoietic Cell Transplantation at Screening
- Type of Conditioning Regimen, n (%)
- Reduced intensity conditioning regimen
- Any aGVHD at Screening, n (%)
- Any cGVHD at Screening, n (%)
- Donor Recipient HLA Match, n (%)

3.3.3 Prior and Concomitant Medications/Procedures

Concomitant medications will be coded to anatomical therapeutic chemical (ATC) class and preferred term using the WHO Drug Dictionary. All medications taken prior to the first dose of study treatment will be considered as prior medications. The medications taken prior to the first dose of study treatment and were ongoing or started on or after the first dose of study treatment will be considered as concomitant medications.

The numbers and percentages of participants taking prior and concomitant medications by ATC class and preferred term will be summarized based on the Safety Population.

3.4 Efficacy Analyses

Only the primary efficacy endpoint will be summarized for the primary treatment period based on the mITT Population.

For AdV viral endpoints at Day 29 or Week 4 visit, a +14-day window will be applied to the Day 29 visit. The last observed plasma AdV DNA result through Day 29 + 14 days (up to 43 days post first infusion) will be used for the analysis for all the participants including those who crossover from PSL to placebo. For participants who crossover from placebo to PSL, the pre-dose cross-over Day 1 viral load may be used. Participants who cross over on or before Day 29 will be treated as failure.

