## 2 SCHEDULE OF ACTIVITIES

**Table 1. Schedule of Activities for Primary Study Period**

Study Week (Primary Study Period)	1	2	3	4	5	6	7	8	9	10	11	12
Study Day (Primary Study Period)	1	2	3	4	5	6	7	8	9	10	11	12
Visit Window (Days)	NA	NA	±2	±2	±3	±3	±3	±5	±5	±28	±28	±42
Study Procedures												
Informed consent/assent	X											
I/E criteria	X	X										
Demographics and medical history [2]	X											
HLA match for cell line selection	X											
Randomization	X											
Prior and concomitant medications	X	X	X	X	X	X	X	X	X	X	X	X
SARS-CoV-2 PCR virus assessment (nasal/nasopharyngeal swab)	X											
FSH test [3]	X											
Pregnancy test [4]	X	X			X				X	X	X	X
Study treatment administration [5]		X			X							
Infusion site evaluation [6]		X			X							
Post-infusion monitoring [7]		X			X							
COA (EQ-5D) [8]		X					X		X		X	X
Adverse events	X	X	X	X	X	X	X	X	X	X	X	X
Hospital information [9]	X	X	X	X	X	X	X	X	X	X	X	X
Physical examination [10, 11]	X	X	X	X	X		X				X	X
Height and weight [12]	X	X									X	X
Vital signs including SpO 2 [11, 13]	X	X	X	X	X	X	X	X	X	X	X	X
12-lead ECG [14]	X	X			X							
Chest X-ray and/or CT scan [15]	X						X					
Urinalysis [16]	X	X					X				X	X
Hematology and clinical chemistry [16]	X	X	X	X			X		X	X	X	X
Coagulation (PT, INR, and PTT)		X					X					

Study Week (Primary Study Period)	■■■	■■■	■■■	■■■	■■■	■■■	■■■	■■■	■■■	■■■	■■■	■■■	
Study Day (Primary Study Period)	■■■	■■■	■■■	■■■	■■■	■■■	■■■	■■■	■■■	■■■	■■■	■■■	
Visit Window (Days)	NA	NA	±2	±2	±3	±3	±3	±5	±5	±28	±28	±42	NA
Study Procedures													
[16]													
Adenovirus viral load in blood and stool with viral DNA extraction and storage [16, 17]	X	X	X	X	X	X	X	X	X	X	X	X	
Adenovirus viral load in urine [16, 18]								X					
BKV, CMV, JCV, EBV, and HHV-6 viral load in blood [16, 19]	X	X			X		X		X	X	X	X	
Adenovirus viral load in nasopharyngeal swab	X						X						
Adenovirus viral load in BAL fluid and/or CSF [16, 20]								X					
Bank PBMCs for VST persistence and plasma for cytokine evaluation [16, 21]		X			X		X		X	X	X	X	
Acute GVHD evaluation [22]	X	X	X		X		X			X	X	X	
Chronic GVHD evaluation [22]										X	X	X	

Note: Participants may return to the clinical site more frequently as determined by their clinical condition at the discretion of the Investigator and in collaboration with the Medical Monitor.

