**5.2 Participant and Study Completion**

Approximately 115 participants will be screened to achieve 82 randomly assigned to study treatment and dosed to obtain an estimated total of 41 participants per treatment group evaluable for the primary endpoint.

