### Amendment 4 Rationale

Major Revisions include:

- **Addition of Interim analysis (sample size re-estimation and futility analysis)**

Rationale: AlloVir has decided to add back in the interim analysis for a sample size re-estimation and futility analysis that were originally planned to address the lack of adequate published data on the natural history of AdV infection in a similar patient population as those enrolled into the AdV Ph3 study. The SSRE/futility assessment will provide an opportunity to increase the sample size and the study power to detect a treatment response based on the interim data.

- **Changes in Sample Size Determination**

Rationale: The assumptions in sample size determination were updated to be more conservative. The method of the sample size calculation is changed to a Chi-square test because the sample size is sufficient to use this method and it is consistent with the test used for logistic regression model of the primary analysis. Patients who drop out will be included in the analysis, therefore, the dropout rate is not considered in the calculation.

- **Changes in Primary Analysis**

Rationale: Based on published data absolute lymphocyte count is believed to be a strong predictor of clinical outcome, therefore it has been included as a covariate in the model for post-randomization adjustment.

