3.4.1 Primary Efficacy Endpoint Analysis

3.4.2 Primary Analysis of Primary Efficacy Endpoint

The primary efficacy endpoint, undetectable viremia (less than LLOQ) at Day 29 of the Primary Study Period, will be summarized by treatment group using the count and percentage, together with an exact (Clopper-Pearson) 95% confidence interval for the true percentage. The difference in percentages between the two treatments (posoleucel – placebo), together with a 95% exact confidence interval for the true difference, will be presented.

This endpoint will be analyzed using logistic regression. The model will include a term for treatment and the following covariates: level of viremia at Baseline ($\geq 10,000$ copies/mL or $< 10,000$ copies/mL AdV DNA), age (≥ 12 years or < 12 years) and absolute lymphocyte count at Baseline. For participants who discontinued treatment but remain on the study, data collected after treatment discontinuation will be included in the analysis. If a participant doesn't have plasma AdV DNA result in the Day 29 through Day 43 window but has undetectable viremia before Day 29 and after Day 43, it will be imputed as success for the primary endpoint. The deaths related to adenovirus infection on or before Day 29 will be imputed as failure.

Subgroup analyses of the primary endpoint will be performed for both of the randomization stratification variables: (1) level of viremia: $\geq 10,000$ copies/mL and $< 10,000$ copies/mL AdV DNA and (2) age: ≥ 12 years or < 12 years.

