Appendix 1 Analysis Visit Windows

Table 1 Analysis Visit Windows for Adenovirus Viral Load Data

Nominal Visit	Nominal Study Day	Visit Window Study Day	
		Lower Limit	Upper Limit
Day 1/Baseline	1		≤1
Week 1	8	2	11
Week 2	15	12	18
Week 3	22	19	25
Week 4	29	26	32
Week 5	36	33	39
Week 6	43	40	57
Week 10	71	58	92
Week 16	113	93	141
Week 24	169	>141	

Table 2. Analysis Visit Windows for Other Viral Load and Clinical Lab

Nominal Visit	Nominal Study Day	Visit Window Study Day	
		Lower Limit	Upper Limit
Day 1/Baseline	1		≤1
Week 1	8	2	11
Week 2	15	12	22
Week 4	29	23	36
Week 6	43	37	57
Week 10	71	58	92
Week 16	113	93	141
Week 24	169	>141	

Signature Page for P-105 303 Final SAP v1.0 for abbreviate CSR
VV-CLIN-000364 v1.0

Approval Task	[REDACTED] ics 12-Jan-2024 19:11:42 GMT+0000
---------------	---

Approval Task	[REDACTED] 12-Jan-2024 21:26:04 GMT+0000
---------------	---

Signature Page for P-105 303 Final SAP v1.0 for abbreviate CSR
VV-CLIN-000364 v1.0

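### The SAP does not fix one window for the Day 29 viremia result, and it leaves most dosed participants with no in-window result unscored

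*SAP*

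**What the plan says.** Four parts of the SAP bear on which plasma AdV result enters the primary endpoint.

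- **SAP 3.4** applies a +14-day window to the Day 29 visit and adds: "The last observed plasma AdV DNA result through Day 29 + 14 days (up to 43 days post first infusion) will be used". Protocol 10.3.1 has the same rule. Neither names an earliest day.
- **SAP 3.4.2** deals with a participant who "doesn't have plasma AdV DNA result in the Day 29 through Day 43 window". Such a participant is a success if viremia was undetectable both before Day 29 and after Day 43. AdV-related death by Day 29 is a failure. Under 3.4, so is cross-over by Day 29.
- **SAP 3.1.2 and Appendix 1 Table 1** ("Analysis Visit Windows for Adenovirus Viral Load Data") assign every visit to an analysis window. Week 4 is Day 26 to 32, and the assessment closest to Day 29 is used.
- **SAP 3.1.4** sets the default: "data will be analyzed and presented as observed and will not be imputed for the analysis of efficacy and safety", unless another section says otherwise.

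On who should be counted, SAP 3.2.2 says "The mITT Population will include all randomized participants who receive at least one dose of posoleucel or placebo". Protocol 5.2 expects 82 dosed participants to yield "an estimated total of 41 participants per treatment group evaluable for the primary endpoint". The Amendment 4 rationale for the current sample size says "Patients who drop out will be included in the analysis, therefore, the dropout rate is not considered in the calculation".

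**The concern.** Two things are unsettled for the only efficacy endpoint that this SAP reports.

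The first is the start of the window. Protocol Table 1 appears to allow the Day 29 visit within 3 days either way, and SAP Table 1 accepts Days 26 to 28 as Week 4. SAP 3.4.2 treats a sample on those days as outside the window, and no sentence gives precedence.

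The second is the empty window. Beyond the success imputation, AdV-related death by Day 29 and cross-over by Day 29, no outcome is assigned. A participant who withdraws early, or dies of another cause, is then left out. The rules are also lopsided. Undetectable on both sides of the gap counts as success, but detectable on both sides has no matching failure rule.

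At stake are the numerator and denominator of the percentages, exact confidence intervals, treatment difference, logistic model and subgroup results. Two programmers working from the same SAP could report different figures.

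**Working it through.** **Sample size, as context.** The protocol's inputs are 0.55 v 0.25, two-sided alpha 0.05, 80% power, 1:1 allocation and a chi-square test. With mean rate 0.40:

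n = [1.96 × √(2 × 0.40 × 0.60) + 0.8416 × √(0.55 × 0.45 + 0.25 × 0.75)]² / 0.30² = (1.358 + 0.555)² / 0.09 = 40.7

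This rounds up to 41 per arm, 82 in total, as stated. It contains no allowance for missing outcomes. (SAP 2.2.4 gives 0.50 for posoleucel, which is a separate matter. The protocol rates are used here.)

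**Last available sample by Day 43, under each rule**

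| Study day of last sample | 3.4 with 3.4.2 (Day 29–43) | SAP Table 1 |
|---|---|---|
| 25 or earlier | outside | Week 3 or earlier |
| 26–28 | outside | Week 4 |
| 29–32 | inside | Week 4 |
| 33–43 | inside | Week 5 or 6 |

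**When a Day 26–28 sample is the last one.** Nominal days come from SAP Table 1. Visit tolerances are read from the column order of protocol Table 1, whose day headings are not legible.

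- Day 29 ± 3 = Days 26–32: 3 of the 7 permitted days precede Day 29.
- Week 5, Day 36 ± 5 = Days 31–41: all 11 days lie within Day 29–43.
- Week 6, Day 43 ± 5 = Days 38–48: 5 of 11 days (44–48) fall after Day 43.

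An on-time Week 5 sample therefore always fills the window. The problem arises only if Week 5 is missed or the participant has left, and Week 6 does not always rescue it.

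**Effect of leaving one participant out.** Assume 20 per arm (about 40 at the interim, 1:1). The protocol rates give 0.55 × 20 = 11 and 0.25 × 20 = 5. With everyone scored, the difference is 11/20 − 5/20 = 30.0 points.

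| Participant left out | Calculation | Difference (points) |
|---|---|---|
| One posoleucel success | 10/19 − 5/20 | 27.6 |
| One placebo success | 11/20 − 4/19 | 33.9 |
| One posoleucel failure | 11/19 − 5/20 | 32.9 |
| One placebo failure | 11/20 − 5/19 | 28.7 |
| Two posoleucel successes | 9/18 − 5/20 | 25.0 |
| Two placebo successes | 11/20 − 3/18 | 38.3 |

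At 41 per arm (23/41 − 10/41 = 31.7), leaving out one success gives 22/40 − 10/41 = 30.6 or 23/41 − 9/40 = 33.6.

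**Upper limit.** SAP 3.1.1 makes the first dose Day 1, so Day 29 is 28 days after it and Day 29 + 14 = Day 43 is 42 days after it. The parenthesis in 3.4, 43 days after first infusion, is Study Day 44. This matters only for a sample taken on Day 44.

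**The case against.** The sponsor can fairly say that 3.4 and 3.4.2 agree. A plus-14-day window on the Day 29 visit runs forward from Day 29, and 3.4.2 simply names it. The Amendment 3 rationale supports this, since the window was added for clearance delayed past Day 29. That stands.

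A reader might infer that 3.4, having no start day, carries any earlier result forward, so that a Day 8 value could stand in for Day 29. The documents do not support this. A last undetectable result before Day 29 would then already be a success, and most of the 3.4.2 imputation would be redundant. Nor do the sections name three different start days: 3.4 names none, and Table 1 is a general visit map.

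The sponsor can add that as-observed is a stated rule, that mITT membership does not require an observed outcome, that protocol 5.2 gives an estimate only, and that the Amendment 4 rationale was written for the full analysis, before the futility stop. This weakens the conflict but does not remove it. The rationale explains why the current sample size has no dropout allowance, and the reduced SAP neither withdraws that intent nor says that dosed participants without a result are excluded.

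The size of the effect is also open to challenge. At 11/20 v 5/20 the approximate 95% half-width is 1.96 × √(0.55 × 0.45/20 + 0.25 × 0.75/20) = 28.9 points, far more than one participant moves the difference.

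**Conclusion.** The point holds in a limited form. The natural reading of the SAP is Day 29 to 43. On that reading, an on-time Day 26 to 28 sample with nothing later by Day 43 is not counted, although Table 1 calls it Week 4 and no sentence says which governs. Participants with an empty window outside the three special rules are left out by default, against the stated intent that dropouts are included.

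The number affected is not given and is probably small, because an on-time Week 5 sample settles the matter. At the assumed 20 per arm, one participant left out moves the difference by about 1 to 4 points, in either direction. This rests on the protocol planning rates and on visit tolerances read from column order. Only the 3-day tolerance for Day 29 chest imaging is written out, in protocol 9.1.3.

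A reader might infer bias towards one arm, or doubt about the futility stop. Neither is supported. The direction is unknown, SAP 3.1 plans no hypothesis tests, and the futility rules sit in a separate plan. The consequence is for the accuracy and reproducibility of the reported estimates.

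**What to change.** 1. Keep the last-result rule and give one window, Study Day 26 to 43, in both 3.4 and 3.4.2. Because the last result is used, a Day 26 to 28 sample counts only when nothing later exists by Day 43. The success imputation then refers to undetectable results before Day 26 and after Day 43.
2. State that this window overrides 3.1.2 and Table 1 for the primary endpoint.
3. Score mITT participants with no in-window result as failures unless the success imputation applies, and report their number per arm.
4. Change the parenthesis to Study Day 43 (42 days after first infusion).

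If the database is already locked, record the window and scoring actually used in the CSR, as SAP section 1 provides for deviations. No extra sensitivity table is needed.

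The cost is a few sentences and one count per arm from data already collected. There are two drawbacks. A Day 26 start changes the only explicit start day for this endpoint, after the futility stop, and must be recorded as a change to 3.4.2. Failure scoring is a choice that lowers the percentage in any arm with empty windows, which is why the counts should be shown.
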